#### 7.3. PK Endpoints

Serum pharmacokinetic parameters including the maximum concentration (Cmax), time to maximum concentration (Tmax), and area under the concentration versus time curve (AUClast, AUC $\tau$ ) for PF-06747143 will be estimated using non compartmental analysis. If data permit, area under the concentration versus time curve to infinity (AUCinf), terminal elimination half life (t1/2), clearance (CL), apparent volume of distribution (Vss), and accumulation ratio (Rac) will be also estimated. The PK parameters will be summarized descriptively by dose, cycle and day.

PF0-06747143 concentrations will be summarized descriptively (n, mean, SD, coefficient of variation(CV), median, minimum, maximum, geometric mean and its associated CV) by dose, cycle, day and nominal time. Individual patient and median profiles of the concentration time data will be plotted by dose, cycle and day (single dose and steady state) using nominal times. Individual and median profiles will be presented on both linear linear and log linear scales.

Dose normalized AUCinf (AUC $\tau$  at steady state), and Cmax will be plotted against dose (using a logarithmic scale) by cycle and day. These plots will include individual patient values and the geometric means for each dose. These plots will be used to help understand the relationship between the PK parameters and dose.

The observed accumulation ratio will be summarized descriptively. Each will be analyzed after natural log transformation using a one way analysis of variance with a single term for dose. The means and 90% confidence intervals (CIs) obtained from the model will be back transformed to provide means and 90% CIs for the accumulation for each dose.

Trough concentrations will be plotted for each dose using a box whisker plot by cycle and day within cycle in order to assess the attainment of steady state.

#### 7.5. Covariates

Not applicable.

#### 8. HANDLING OF MISSING VALUES

#### 8.1. Missing Dates

In compliance with Pfizer standards, if the day of the month is missing for any date used in a calculation, the 1st of the month will be used to replace the missing date unless the calculation results in a negative time duration (eg, date of onset cannot be prior to day one date). In this case, the date resulting in 0 time duration will be used. Pfizer standards are also used if both month and day are missing (Jan 1 unless negative time duration). This excludes the pharmacokinetic, ECG, and pharmacodynamic analyses, which will only use the actual date collected or if date not available deem the data missing.

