#### **Primary Endpoints**

 Adverse Events as characterized by type, frequency, severity (as graded by National Cancer Institute Common Terminology Criteria for Adverse Events (NCI CTCAE) v. 4.03), timing, seriousness, and relationship to study therapy;

- Laboratory abnormalities as characterized by type, frequency, severity (as graded by NCI CTCAE v.4.03) and timing;
- Preliminary evidence of anti-leukemia activity including objective disease response; as assessed using the standardized response criteria including objective response rate (ORR), duration of ORR, and relapse free survival (RFS).(Ref 2)

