**Progression Free Survival (PFS)** - is defined as the time from Cycle 1 Day 1 (C1D1) to first documentation of disease progression or to death due to any cause, whichever occurs first. Subjects last known to be 1) alive 2) on treatment or within the post-treatment follow-up period and 3) progression-free, are censored at the date of the last disease assessment that verified lack of disease progression. Subjects who start new anti-cancer treatment prior to the end of post-treatment follow-up period and have adequate baseline and on-treatment objective disease assessments without evidence of progressive disease are censored at the date of the last objective disease assessment. Subjects with inadequate baseline or no on-study disease assessments are censored at C1D1 unless death occurred prior to the first planned assessment (in which case the death is an event). Subjects with at least one on-study disease assessment who discontinue treatment without disease progression and without death within 28 days of discontinuation are censored at the date of the last objective disease assessment that verified lack of disease progression (if progression or death is within 28 days of discontinuation the progression or death is an event). Subjects with documentation of progression or death after an unacceptably long interval (>16 weeks) since the previous disease assessment will be censored at the time of the previous assessment.

PFS (days) = [progression/death date - C1D1 + 1].

• Overall survival (OS) is defined as the time from initial dose until death from any cause, and is measured in the intent-to-treat population.

More details of censoring are provided in Appendix 2.

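### Partial death dates are set to the 1st of the month or 1 January with no lower bound at last known-alive contact, so OS and PFS events can be dated too early

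*SAP*

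**What the plan says.** SAP Section 8.1 applies "if the day of the month is missing for any date used in a calculation". The missing day is replaced by the 1st "of the month will be used to replace the missing date unless the calculation results in a negative time duration". When the limit is reached, "In this case, the date resulting in 0 time duration will be used". For a missing month and day, "Pfizer standards are also used if both month and day are missing (Jan 1 unless negative time duration").

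The stated exemption is narrow: "This excludes the pharmacokinetic, ECG, and pharmacodynamic analyses, which will only use the actual date collected". Death, progression and relapse dates are not exempt.

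The durations concerned are defined in Section 7.1. For PFS, "PFS (days) = [progression/death date - C1D1 + 1"]. For survival, "Overall survival (OS) is defined as the time from initial dose until death from any cause". Relapse-free survival is among the Part 2 primary endpoints in Section 2.4.

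Section 8.2 refers efficacy to the censoring tables in Appendix 2 (Section 11.2). Those tables use the date of death or the date of a disease assessment. They have no rule for partial dates and no bound at the last date the patient was known to be alive.

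**The concern.** The only check on an imputed date is that the duration is not negative. For OS and PFS the starting point is the first dose, so any date from first dose onwards passes, including one that falls before a visit at which the patient was seen alive. The analysis data can then contradict the visit records, and the time to event is too short.

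Event status can change as well. Section 7.1 counts a death within 28 days of stopping treatment as a PFS event and otherwise censors at the last disease assessment. A missing day can move a death by up to 30 days, which is longer than that window.

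**Working it through.** The SAP gives no figure to reproduce on this point. The check applies the Section 8.1 rule literally to assumed dates, with and without a lower bound at the last known contact.

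**Inputs.** From the SAP: the imputation rule (Section 8.1), PFS days = event date − C1D1 + 1 (Section 7.1) and the 28-day window (Section 7.1, Appendix 2). Assumed: all calendar dates below, and uniform true dates for the averages.

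**Example A: C1D1 10 March 2016, last contact alive 20 September 2016 (day 195).**

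| Death recorded as | Rule as written | Distance before last contact | With lower bound |
|---|---|---|---|
| September 2016 | 1 September 2016, day 176 | 195 − 176 = 19 days | 20 September 2016, day 195 |
| 2016 only | 1 January precedes C1D1, so 10 March 2016, day 1 | 195 − 1 = 194 days | 20 September 2016, day 195 |

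In the second row the elapsed time is 0, or 1 day under the PFS formula with its + 1. Taken literally, the date giving exactly 0 under that formula is 9 March, the day before C1D1.

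**Example B: C1D1 10 November 2015, same last contact, death recorded as 2016 only.** The rule gives 1 January 2016, day 53. The last contact is day 316, so the imputed death is 316 − 53 = 263 days before it. With the bound, the date is 20 September 2016, day 316.

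**Example C: the 28-day window.** Treatment is stopped on 20 August and the true death is on 28 September, 39 days later, so PFS should be censored. If the date is recorded only as September, the rule gives 1 September, 12 days after stopping, and the patient becomes a PFS event. If the patient was documented alive on 20 September, the bounded date is 31 days after stopping and the patient stays censored. Without any documented contact beyond the window, the bound would not correct this case.

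**Average shift if true dates are uniform (assumption).**
- Day missing, over a 365-day year: a month of k days contributes k(k − 1)/2. The sum is 7 × 465 + 4 × 435 + 378 = 5,373, and 5,373/365 = 14.7 days, with range 0 to 30.
- Month and day missing, origin in an earlier calendar year: (0 + 364)/2 = 182 days, with range 0 to 364.
- Month and day missing, origin in the same calendar year: the limit applies, duration becomes zero, and the shift is the patient's whole event time.

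**The case against.** Several counter-arguments have force.

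- **Progression and relapse.** Appendix 2 dates progression at the disease assessment that first shows it, from investigator assessments on the CRF (Section 7.1). Such dates are unlikely to be partial. This stands: the realistic exposure is death dates, mainly for OS.
- **PFS deaths.** Deaths after discontinuation count only within 28 days, and Section 2.2.3 provides 60 days of follow-up, so a death known only by year is unlikely there. This also stands, although a missing day alone is enough to cross the window, as Example C shows.
- **Direction.** A reader might infer that the rule biases every duration downward. It does not. A partial start date, such as first response for duration of response, also moves earlier, and that lengthens the duration. The shortening holds for partial event dates measured from a known origin.
- **New therapy.** A reader might infer that early imputation of new-therapy dates causes early censoring throughout. Table 4 (PFS and duration of response) has no new-therapy row. Table 5 (time to progression) does, but it censors at the last assessment before the new therapy, as the Section 7.1 text does for PFS, so a small date error often changes nothing.
- **Consequence.** Sections 4.1 and 9.1 rule out hypothesis testing, and OS, although defined in Section 7.1 and summarised under Section 9.2.2.1, is not a listed endpoint in Section 2.3.2 or 2.4. The rule is also a declared sponsor standard. These points limit the importance, but they do not supply the missing bound.

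**Conclusion.** The point holds for partial death dates and, if they ever occur, partial progression or relapse dates. As written, the rule can place such an event before a documented later contact or event-free assessment, shorten OS or PFS, and turn a censored PFS time into an event.

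The average shifts of 14.7 and 182 days rest on uniform true dates, and the second also needs an origin in an earlier calendar year. The SAP does not say how many dates will be partial. A reader might infer that medians in cohorts of up to 30 patients would move materially; nothing in the SAP establishes that, and no median was calculated under any assumed frequency. With descriptive analyses the impact is probably small, so this is a minor improvement.

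**What to change.** Add one sentence to SAP Section 8.1. For a partial death date, use the later of the imputed date and the last date the patient was documented alive. For a partial progression or relapse date, should one occur, use the later of the imputed date and the last event-free assessment. Keep the result within the known month or year, and flag imputed dates in the listings.

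The bound should be the last known-alive or event-free date itself. Using the following day could leave the known month: a September death with a contact on 30 September would become 1 October.

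Keep the sponsor standard for all other dates, including new-therapy dates. A last-alive bound would misdate those: therapy begun in September in a patient followed alive to March would be given a March start.

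The cost is that sentence and a small derivation step that departs from the sponsor standard. Section 9.2.2.1 already plans to list the most recent progression-free date and the last assessment date; the last known-alive date would be taken from the visit records.

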#### 8.2. Efficacy Analysis

Censoring rules for time-to-event endpoints are detailed in Section 11.2 Appendix 2.

#### 8.3. Pharmacokinetics

#### Concentrations below the limit of quantification

In all data presentations (except listings), concentrations below the limit of quantification (BLQ) will be set to zero. (In listings BLQ values will be reported as "<LLQ", where LLQ will be replaced with the value for the lower limit of quantification.).

#### **Deviations, missing concentrations and anomalous values**

In summary tables and plots of median profiles, statistics will be calculated with concentrations set to missing if one of the following cases is true:

- a. A concentration has been reported as ND (ie, not done) or NS (ie, no sample),
- b. A deviation in sampling time is of sufficient concern or a concentration has been flagged anomalous by the pharmacokineticist.

Note that summary statistics will not be presented at a particular time point if more than 50% of the data are missing.

#### Pharmacokinetic parameters

Actual PK sampling times will be used in the derivation of PK parameters.

If a PK parameter cannot be derived from a subject's concentration data, the parameter will be coded as NC (ie, not calculated). (Note that NC values will not be generated beyond the day that a subject discontinues).

In summary tables, statistics will not be presented for a particular treatment group if more than 50% of the data are NC. For statistical analyses, PK parameters coded as NC will also be set to missing.

If an individual subject has a known biased estimate of a PK parameter (due for example to an unexpected event such as vomiting before all the drug is absorbed in the body), this will be footnoted in summary tables and will not be included in the calculation of summary statistics or statistical analyses.

#### **QTc**

For the QTc analyses, no values will be imputed for missing data.

C

#### 9. STATISTICAL METHODOLOGY AND STATISTICAL ANALYSES

#### 9.1. Statistical Methods

No formal hypothesis testing will be performed in this exploratory study.

#### **Analyses of Time-to-Event Endpoints**

Time-to-event endpoints will be summarized using the Kaplan-Meier method and displayed graphically when appropriate. Median event times and 2-sided 95% confidence intervals for each time-to-event endpoint (Brookmeyer and Crowley, 1982) will be provided.

#### **Analyses of Binary Endpoint**

The rates of binary endpoints will be provided along with the corresponding 2-sided 95% confidence intervals using an exact method.

#### **Analyses of Continuous Data**

Descriptive statistics, such as the mean, standard deviation, coefficient of variation, median, minimum, and maximum values, will be provided for continuous endpoints.

#### 9.2. Statistical Analyses

#### 9.2.1. Primary Analysis

Dose Limiting Toxicity (DLT) is the primary endpoint of the dose escalation component of the study, which will be summarized by dose level using the Per Protocol Analysis Set for patients in the dose escalation portion of the study. A listing of the DLTs will also be provided.

If necessary, a summary and listing of the DLT by malignancy may be provided using the Per Protocol Analysis Set for patients in the MTD expansion portion of the study.

#### 9.2.2. Secondary Analyses

#### 9.2.2.1. Efficacy Analysis

In this Phase 1 study efficacy is a secondary objective. Note that the efficacy analysis is to be conducted by malignancy for patients in the MTD expansion cohorts who are in the Safety Analysis Set and have baseline disease assessment and at least one post-baseline disease assessment. In the event that a large number of patients in the escalation portion of the study have the same malignancy, the efficacy analysis may be conducted.

Summary tables of best Overall Response Rate, Progression Free Survival, and Overall Survival will be provided overall and by malignancy. Efficacy listings will be provided that include best response, first CR/PR date, last date with CR or PR, most recent date without progression, progression date, death date, date of first response and last tumor assessment date, etc.

A response rate overall for Part 1 dose escalation and response rates by low, medium, and high dose groups may be presented.

The following table provides an overview of the efficacy analysis.

**Endpoint Analysis Set** Interpretation **Statistical** Model/ Missing Method Covariates/ Data Strata By dose range/ Overall Per Protocol, Exact CI Censored Secondary response expansion malignancy per Section Analysis 11.2 cohorts, etc. Progression Per Protocol, Kaplan-By malignancy Censored Secondary Free Survival expansion per Section Meier Analysis (PFS) cohorts 11.2 Per Protocol, By malignancy Censored Secondary Time to Kaplan-Progression expansion Meier per Section Analysis cohorts 11.2 (TTP) Duration of Per Prtocol, By malignancy Censored Secondary Kaplan-Response (DR) expansion Meier per Section **Analysis** cohorts 11.2

**Table 2.** Overview of Efficacy Analysis

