#### 4. HYPOTHESES AND DECISION RULES

#### 4.1. Statistical Hypotheses

There are no statistical hypotheses. The emphasis of the final analyses will be on estimation of key summary statistics.

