#### 6.2. 'PER PROTOCOL' Analysis Set

The per protocol analysis set includes all enrolled patients who receive at least one dose of study treatment at the dose level of MTD and who do not have major treatment deviations during first cycle. Patients with major treatment deviations in Cycle 1 are not evaluable for the MTD assessment and may be replaced. Major deviations include failure to satisfy major entry criteria (eg, confirmation of the target disease population; signed informed consent), administration of less than 3 out of the 4 doses in Cycle 1 or 80% of the planned Cycle 1 dose (provided that the reduction is not due to toxicity attributable to PF-06747143) or use of

other anti-cancer/anti-leukemia treatments during the active treatment and disease follow up phases other than as defined/allowed in this protocol.

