#### 11.2. APPENDIX 2: CENSORING DETAILS

Table 4. Progression Free Survival and Duration of Response

Situation	Date of Progression/Censoring 	Outcome		
Inadequate baseline assessment	Start date (C1D1)	Censored		
No on-study assessments	Start date (C1D1)	Censored		
Alive, on treatment  and no Progression	Date of last objective tumor assessment	Censored		
Progression Documented on or between scheduled tumor assessments prior to treatment discontinuation 	Date of first objective tumor assessment showing objective progression	Progressed (Event)		
Treatment discontinuation for undocumented progression	Date of last objective tumor assessment prior to discontinuation 	Censored		
Treatment discontinuation due to toxicity or other reason	Date of last objective tumor assessment prior to discontinuation 	Censored		
Death prior to first planned tumor assessment	Date of death	Death (Event)		
Death without objective progression prior to treatment discontinuation 	Date of death	Death (Event)		
Death or progression after 2 or more missed tumor assessments	Date of last objective tumor assessment prior to the event	Censored		

1: For date of censorship, if a tumor assessment takes place over a number of days (eg, superficial lesions one day, scans another), the last date is used as the assessment date.

**Table 5.** Time to Progression

Situation	Date of Progression/Censoring 	Outcome		
Inadequate baseline assessment	Start date (C1D1)	Censored		
No on-study assessments	Start date (C1D1)	Censored		
Alive, on treatment  and no	Date of last objective tumor assessment	Censored		
Progression	-			
Progression Documented on or	Date of first objective tumor assessment	Progressed (Event)		
between scheduled tumor assessments	showing objective progression			
prior to treatment discontinuation 				
Treatment discontinuation for	Date of last objective tumor assessment	Censored		
undocumented progression	prior to discontinuation 			
Treatment discontinuation due to	Date of last objective tumor assessment	Censored		
toxicity or other reason	prior to discontinuation 			
New anticancer treatment <28 days	Date of last objective tumor assessment	Censored		
after discontinuation of treatment	prior to new anticancer treatment			
without progression				
Death prior to first planned tumor	Start date (C1D1)	Censored		
assessment				

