#### 11.4. Disease Assessment

The following section describes the CRFcompletion guidelines and the corresponding response criteria.

If assessment was done, place 'X' in one box only (unless otherwise specified for that selection), to record the disease assessment. Select from the following:

1. Morphologic Complete Remission (CR): This is morphologic leukemia-free state with bone marrow blasts < 5%; absence of blasts with Auer rods; absence of extramedullary disease (EMD); absolute neutrophil count >1000/ul and platelet >100,000/ul; independence from red cell transfusions.

If the CR box is checked, check the box(es) below if patient achieved the following:

- a. Cytogenetic CR (CRc): Reversion to a normal karyotype at the time of morphologic CR, as defined above, in cases with an abnormal karyotype at the time of diagnosis; based on the evaluation of 20 metaphase cells from bone marrow.
- b. Molecular CR (CRm): Reversion to a molecular-negative phenotype at the time of morphologic CR, as defined above.

Note: Even if the CRc and/or CRm box(es) are checked, the CR box must still be checked. OR

2. Morphologic Complete Remission with incomplete blood count recovery (CRi): All CR criteria met except for residual neutropenia (absolute neutrophil count <1000/ul) or thrombocytopenia (plateletes <100,000/ul).

OR

3. Morphologic Leukemia-Free State: Bone marrow blasts <5%; absence of blasts with Auer rods; absence of EMD; no hematologic recovery required.

OR

4. Partial Remission (PR): Absolute neutrophil count >1000/ul and platelet >100,000/ul; bone marrow blasts decreased to 5-25% and  $\geq$ 50% decrease from pre-treatment levels.

OR

5. Partial Remission with incomplete blood count recovery (PRI): residual neutropenia (absolute neutrophil count <1000/ul) or thrombocytopenia (plateletes <100,000/ul); bone marrow blasts decreased to 5-25% and  $\geq$  50% decrease from pre-treatment levels.

OR

- 6. Treatment Failure (TF): If TF box is checked, one of the options below must be chosen:
- a. TF due to resistant disease: Failure to achieve CR, CRi, PR or PR; Only includes patients surviving ≥7 days following completion of initial course of treatment with evidence of persistent leukemia by blood and/or bone marrow examination. Initial course of treatment completion is defined as completion of Cycle 1.

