- b. TF due to aplasia: Deaths occurring ≥7 days following completion of initial course of treatment while cytopenic; with an aplastic or hypoplastic bone marrow obtained within 7 days of death and without evidence of persistent leukemia. Initial course of treatment completion is defined as completion of Cycle 1.
- c. TF indeterminate cause: Deaths occurring before completion of therapy, or < 7 days following its completion; or deaths occurring ≥7 days following completion of initial course of treatment with no blasts in the blood, but no bone marrow examination available. Initial course of treatment completion is defined as completion of Cycle 1. Note: If TF applies, the TF box should always be checked along with one of the three options.

OR

7. Relapse: Bone Marrow blast  $\geq$  5%; or reappearance of blast in the blood; or development of EMD

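### SAP Section 9.2.2.1 fixes neither the analysis set nor the missing-data rule for overall response: text and Table 2 name different sets, and the censoring entry cannot apply to a proportion

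*SAP*

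**What the plan says.** **Set in the text.** Section 9.2.2.1 restricts the efficacy analysis to patients in the MTD expansion cohorts "who are in the Safety Analysis Set and have baseline disease assessment and at least one post-baseline disease assessment".

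**Set and missing-data rule in Table 2.** The overall-response row survives only as a flattened string: "Overall Per Protocol, Exact CI Censored Secondary response expansion malignancy per Section Analysis 11.2 cohorts, etc". The column layout was lost when the PDF was read. Three entries can still be assigned to overall response: a Per Protocol set, an exact confidence interval, and missing data censored under Section 11.2. The PFS, TTP and duration-of-response rows carry the same set and the same missing-data entry.

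**Per Protocol (Section 6.2).** This set requires a dose at the MTD level and no major deviation in Cycle 1. Major deviations include failing a major entry criterion and "administration of less than 3 out of the 4 doses in Cycle 1 or 80% of the planned Cycle 1 dose", unless the shortfall is due to toxicity attributable to the study drug. No disease assessment is required.

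**Section 11.2.** Section 8.2 describes it as the place for time-to-event censoring rules. It holds Table 4, titled "Progression Free Survival and Duration of Response", and Table 5, on time to progression.

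**Response form (Section 11.4).** It begins "If assessment was done, place 'X' in one box only" and includes the category "TF indeterminate cause: Deaths occurring before completion of therapy, or < 7 days following its completion".

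**What is fixed elsewhere.** Section 7.1 requires confirmed best response, Section 11.4 lists the categories, and Section 9.1 calls for an exact two-sided 95% interval for binary endpoints.

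**The concern.** A response rate needs a denominator and a rule for patients whose response is unknown. Section 9.2.2.1 gives two denominators, and its only missing-data rule belongs to a different type of endpoint. Two analysts following the SAP could report different rates and intervals from the same data, and both could claim to have followed the plan.

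This carries weight because Section 2.4 lists objective response rate among the Part 2 primary endpoints. Section 4.1 states no hypotheses and says: "The emphasis of the final analyses will be on estimation of key summary statistics". The rate and its interval are therefore the result itself, with no test standing beside them.

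The patients affected are also informative ones. Someone who dies before a post-baseline assessment cannot have a confirmed response, so removing that person from the denominator can only raise the rate.

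**Working it through.** The SAP states no expected response rate, early-death rate or precision target for overall response, so there is no plan figure to reproduce. The check is a comparison of rules, followed by an illustration.

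**1. Are the two sets the same or nested?** Take four hypothetical treated patients in an expansion cohort:

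| Patient | Text of 9.2.2.1 | Per Protocol (6.2) |
|---|---|---|
| Dosed at the MTD level, adequate Cycle 1, no post-baseline assessment | Out | In |
| Assessed at baseline and later, but two of four Cycle 1 doses for a reason other than drug toxicity | In | Out |
| Assessed at baseline and later, but a major entry criterion failed | In | Out |
| Assessed at baseline and later, but not dosed at the MTD level | In, if counted in the expansion cohort | Out |

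Each set contains patients that the other excludes, so neither is a subset of the other. Section 9.2.2.1 calls neither one primary or sensitivity.

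**2. Can the missing-data entry be carried out?** Consider the situation "Death prior to first planned tumor assessment". Table 4 records an event at the date of death. Table 5 censors at Cycle 1 Day 1. Both answers are a date and an event status; neither says responder or non-responder. No row in either table concerns response, and the binary-endpoint paragraph of Section 9.1 has no rule for a missing response.

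Both tables also have a row for patients without on-study assessments. Under the text's set that row would be empty, so the censoring tables appear to assume a wider population than the text does.

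**3. What could the text's set do to the rate?** Let r be the responders among N patients with a baseline assessment, and k the non-responders dropped for lack of a post-baseline assessment. The rate moves from r/N to r/(N-k), a factor of N/(N-k).

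Inputs:
- N = 30, the upper size of expansion cohorts E1 and E2 (Sections 2.2.2.1 and 2.2.2.2).
- N = 15, the lower size of Cohort 3 (Section 2.2.2.4).
- r and k are assumptions.
- Intervals are Clopper-Pearson: lower limit Beta(0.025; r, n-r+1), upper limit Beta(0.975; r+1, n-r), with n = N-k.

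| N | r | k | Rate | Exact 95% CI | Factor |
|---|---|---|---|---|---|
| 30 | 15 | 0 | 50.0% | 31.3 to 68.7 | 1 |
| 30 | 15 | 1 | 51.7% | 32.5 to 70.6 | 30/29 = 1.034 |
| 30 | 15 | 3 | 55.6% | 35.3 to 74.5 | 30/27 = 1.111 |
| 30 | 9 | 0 | 30.0% | 14.7 to 49.4 | 1 |
| 30 | 9 | 1 | 31.0% | 15.3 to 50.8 | 1.034 |
| 30 | 9 | 3 | 33.3% | 16.5 to 54.0 | 1.111 |
| 15 | 3 | 0 | 20.0% | 4.3 to 48.1 | 1 |
| 15 | 3 | 1 | 21.4% | 4.7 to 50.8 | 15/14 = 1.071 |
| 15 | 3 | 3 | 25.0% | 5.5 to 57.2 | 15/12 = 1.250 |

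The shifts run from 1.0 point (31.0 - 30.0) to 5.6 points (55.6 - 50.0). The interval widths run from 34.7 points (49.4 - 14.7) to 51.7 points (57.2 - 5.5).

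**4. Per Protocol.** Its direction is not fixed. It can drop a patient who dies of leukemia before adequate Cycle 1 dosing, but it can also drop a responder. Losing one responder from 15/30 to an entry-criteria deviation gives 14/29 = 48.3%. The MTD-level condition could remove further patients of either kind, so this example shows direction only.

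**The case against.** **Much of the endpoint is fixed.** Confirmation, categories and interval method are all stated. A reader might infer that the SAP has no usable rule for overall response at all. The documents do not support that: the gap is confined to the analysis set and the missing-data rule.

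**Early deaths may stay in the denominator.** A reader might infer that the plan inflates the response rate. The SAP does not establish this. Section 11.4 classes deaths before completion of therapy as treatment failure, and its closing note asks for that box to be ticked whenever treatment failure applies. Section 7.1 derives efficacy from the investigator's entries on the case report form. On that reading an early death has a form entry, counts as a non-responder, and the shift is zero. This is plausible, but the form's opening words make an entry conditional on an assessment having been done, and nowhere is a treatment-failure entry said to be a post-baseline disease assessment. The consequence is therefore conditional.

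**A set that keeps such patients already exists.** The modified intent-to-treat set in Section 6.4.1 retains patients who progress or die before the first assessment. However, it is offered only for interim analyses and conference presentations, and neither the text of 9.2.2.1 nor Table 2 uses it.

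**The stakes are modest.** There is no formal testing, the activity data are called preliminary, no stated Part 2 threshold depends on the rate, and the listings would allow recalculation. All of this stands and limits the severity. It does not say which rate is the planned one.

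**Conclusion.** Wrong as written. The text of Section 9.2.2.1 and Table 2 name different, non-nested sets for the same analysis, and the missing-data entry for overall response points to rules that cannot be applied to a proportion. Both findings rest on the SAP's wording alone and hold with high confidence. The set conflict also reaches the PFS, TTP and duration-of-response rows; the misfit of the censoring entry is specific to overall response.

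The case for correction is the ambiguity in a listed Part 2 primary endpoint, not a demonstrated bias. An upward shift arises only under the text's set, and only if a treatment-failure entry does not count as an assessment. Its size is illustrative, since response and early-death counts are assumed: zero to 5.6 points in the examples, small against intervals of about 35 to 52 points. This should be fixed before analysis.

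**What to change.** - In both the text of Section 9.2.2.1 and the overall-response row of Table 2, name one set for the expansion cohorts: treated patients (Safety Analysis Set) with a baseline disease assessment.
- State that early death, treatment failure and absence of any post-baseline assessment count as non-response. Put this rule in the overall-response row in place of the reference to Section 11.2.
- Keep the response-evaluable or Per Protocol rate as a sensitivity analysis, labelled as such. If the response-evaluable rate is kept, say whether a treatment-failure entry counts as a post-baseline assessment.
- Make the set named in the PFS, TTP and duration-of-response rows agree with the text. Their censoring entries can stay as they are.

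The cost is SAP wording only, with no new data and no change to conduct. The downside is that the reported response rate may be slightly less favourable than one based on evaluable patients.
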